#### 3.2. Safety outcomes

Device safety will be assessed by the number of reported adverse events (AE) and their severity.

## 4. Study design

### 4.1. General description

This study is a multicenter, prospective, randomized, double-blind, sham-controlled Phase III trial, consisting of the treatment of a single moderate or severe migraine attack (Grade 2 or 3) at home.

### 4.2. Experimental protocol

Patients will be recruited from the research site database and advertising or during a standard care visit at the headache clinic/research site or at an on-demand appointment. They will be screened during a visit at the investigation site (headache clinic or research site).

Inclusion and exclusion criteria will be reviewed, and the eligible patients will be randomized and then trained about the practical use of the Cefaly® Abortive Program device (device handling, electrode placement, etc.). Following that training, they will perform themselves a first 20-minute e-TNS training test session with a verum or a sham training test device to control their ability to use the device appropriately and bear the feeling of the stimulation.

Included patients (who meet all of the study criteria) will be provided with study material (a Cefaly® Abortive Program (treatment) device with accessories and paper documents) for 2 months to be used on an outpatient basis as soon as they experience a moderate or severe migraine headache (Grade 2 or 3).

The overall study flowchart is illustrated in Figure 1. During the different phases the investigator will monitor adverse events (AE).

#### 4.2.1. Recruitment phase

Patients contacted during a standard care visit at the headache clinic/research site or from research site database and advertising will be screened during a visit at the investigation site.

Patient will receive the information and consent documents and have to sign these documents before study procedures are initiated. The patient will be given a unique patient identification (screening) number (mentioned in the header of the patient's CRF). Then, the investigator will verify that the patient meets all the inclusion criteria and none of the 13 first exclusion criteria. If this is the case, the patient will be randomized to either the verum or the sham group and a unique randomization number will be allocated to him/her. This randomization number is mentioned on the sealed kit of investigational devices picked by the investigator and is reported in the patient's CRF. Then, the patient will be trained about the practical use of the Cefaly® Abortive Program device (verum or sham) thanks to an oral explanation, a video and an Instruction sheet. The patient will then perform him/herself a first 20-minute e-TNS training test session with a verum or sham training test device (according to the randomization) to check his/her

ability to use the device appropriately and to bear the sensation of neurostimulation, and therefore that the last exclusion criteria is not met.

Screened patient meeting all inclusion criteria and none of the exclusion criteria are included in the trial and will receive a verum or sham Cefaly® Abortive Program device with accessories to be used at home to treat a single migraine attack and the related paper documents (diary and AE reporting form). The investigator will explain to the patient how to fill in these documents.

The patient will complete a paper practice diary (Example diary) for a simulated migraine during the screening visit, to ensure that he/she fully comprehends the procedure. The investigator or study coordinator will then review this Example diary in details with the patient.

#### 4.2.2. Acute treatment phase

Included patient will be instructed to treat a single qualifying migraine headache within a 2-month period following the screening visit. A migraine headache is a qualifying migraine when all the following criteria are met:

1. The migraine headache severity is moderate or severe (Grade 2 or 3).
2. The migraine headache is associated with at least one of these migraine-associated symptoms: photophobia, phonophobia, nausea, vomiting.
3. The migraine headache started less than four hours ago.
4. No other migraine headache or headache has occurred in the previous 48 hours.
5. The migraine headache is not already resolving on its own i.e. the pain is not already diminishing.
6. No anti-migraine rescue medication has been taken since the beginning of the migraine headache.

In case of qualifying migraine, patient will have to apply the Cefaly® Abortive Program device (verum or sham) for a complete treatment session of 2 hours as soon as the migraine headache is moderate or severe (Grade 2 or 3).

In his/her paper diary, the patient will have to report the following data just before the start of the e-TNS treatment session (baseline data):

- if there is any aura with the qualifying migraine attack
- the headache pain severity on the following scale: 0 = no pain; 1 = mild pain; 2 = moderate pain; 3 = severe pain

---

 if the patient woke up with a migraine, the starting time of the migraine is considered to be at the time of wake-up.

- the migraine-associated symptoms (photophobia, phonophobia, nausea, vomiting) and will specify which associated symptom is the most bothersome symptom (MBS).

Two hours after the beginning of the treatment session, whatever its duration (normally just after removing the device and the electrode if the session ran correctly for 2 hours), the patient will have to report the following data (2-hour data) in his/her diary:

- the headache pain severity on the following scale: 0 = no pain; 1 = mild pain; 2 = moderate pain; 3 = severe pain
- the migraine-associated symptoms (photophobia, phonophobia, nausea, vomiting)

Patients will be instructed NOT to take any anti-migraine rescue medication during the 2-hour treatment session. Medication intake during the 2-hour treatment phase will be considered as a protocol violation.

Devices (verum and sham) are programmed for a unique 2-hour treatment session to be performed at home to treat a qualifying migraine. If the Cefaly® Abortive Program device (verum or sham) stopped during the 2-hour treatment session, it may not be restarted. Duration, intensity and/or interruption will be recorded for each patient thanks to a built-in electronic system in the device.

In any case, as mentioned before, the patient will have to report 2-hour data (headache pain severity and migraine-associated symptoms) 2 hours after the beginning of the treatment session, whatever the duration of the stimulation session.

In his/her paper AE reporting form, the patient will record any adverse event occurring during the treatment phase and is instructed to notify the investigator immediately for any serious adverse event with the stimulation.

The investigator will perform a follow-up phone call during the 2-month period during which the acute treatment phase has to take place.

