#### 4.2.3. Post-treatment phase

Starting two hours after the beginning of the treatment session, the patient is allowed to take anti-migraine rescue medication if and only if the migraine headache pain is moderate or severe, either because there has not been pain relief or because after initial pain relief (no headache or mild headache pain) a moderate or severe headache is resuming.

The patient will have to report the following data in his/her diary at 24 hours after the beginning of the treatment session (24-hour data):

- the rescue medication intake, if any, between 2 hours and 24 hours after the beginning of the treatment session, and, if applicable, the time when the medication was taken
- the headache pain severity on the following scale: 0 = no pain; 1 = mild pain; 2 = moderate pain; 3 = severe pain

- the migraine-associated symptoms (photophobia, phonophobia, nausea, vomiting)

In his/her AE reporting form, the patient will record any adverse event occurring during the 24 hours following the beginning of the treatment session and is instructed to notify the investigator immediately for any serious adverse event with the stimulation.

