### 5.1. Inclusion criteria

The following inclusion criteria apply:

- 1) Age from 18 to 65 on the day of signing the informed consent form
- 2)  $\geq$  1-year history of migraine with or without aura according to the diagnostic criteria listed in ICHD-III beta (2013) section 1, migraine (8), with the exception of aura without headache, hemiplegic migraine and brainstem aura migraine
- 3) Migraine onset before the age of 50
- 4) Having between 2 and 8 moderate or severe migraine attacks (Grade 2 or 3) per month in each of the two months prior to screening
- 5) Patient understands the study procedures, alternative treatments available, and voluntarily agrees to participate in the study by giving written informed consent
- 6) Patient is able to read and understand the written information (instruction sheet, paper diary and AE reporting form)

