## 7. Practical study modalities

### 7.1. Efficacy outcome measures

The treatment efficacy outcomes will be assessed based on the following clinical data.

- **Headache pain severity.** In order to evaluate the modification of pain severity from baseline to 2-hour and 24-hour time points, patients will be asked to note their headache pain intensity on the following scale: 0 = no pain; 1 = mild pain; 2 = moderate pain; 3 = severe pain.
- **Migraine-associated symptoms.** The patient will also note the presence of migraine-associated symptoms (photophobia, phonophobia, nausea, vomiting) and will specify which associated symptom is the most bothersome symptom (MBS) at baseline.
- **Rescue medication intake.** The patient will also record whether he/she took ANY anti-migraine rescue medication during the 24 hours following the beginning of the e-TNS treatment session.

The following table depicts when the different measures will be made:

	At baseline, i.e. just before the beginning of the e-TNS session	2 hours after the beginning of the e-TNS session	24 hours after the beginning of the e-TNS session
Headache pain severity	•	•	•
Migraine-associated symptoms	•	•	•
Identification of the most bothersome migraine-associated symptom (MBS)	•		
Rescue medication intake			•

All clinical data will be collected on a paper diary and AE reporting form.

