### 8.2.4. Statistical analysis

#### Efficacy analysis

The efficacy analysis will be executed on a modified intention-to-treat (mITT) basis.

Patient data will be included in the mITT analysis if all the four following conditions are met:

1. The patient treated a qualifying migraine.
2. The patient applied the Cefaly® Abortive Program treatment (verum or sham) during at least 30 minutes\*.
3. The headache pain severity score **AND** the migraine-associated symptom(s) at baseline were reported in the diary.
4. The headache pain severity score **OR** the migraine-associated symptom(s) at 2 hours were reported in the diary.

\*If the patient stopped the 2-hour treatment session after 30 minutes but before its end for any reason, he/she is kept in the modified intention-to-treat (mITT) analysis if all the other conditions are met.

If the patient takes anti-migraine rescue medication between 2 hours and 24 hours after the beginning of the e-TNS treatment session, the headache pain intensity and migraine-associated symptoms presence

can be affected by the medication and the last value carried forward method (2-hour value carried forward method in this case) will be applied for the 24-hour time point headache pain severity and migraine-associated symptoms.

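### Qualifying criterion 6 looks back for medication only to the start of the headache, so medication taken during a preceding aura is neither excluded nor recorded; the expected effect is a small dilution of the treatment difference

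*Combined protocol and SAP*

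**What the plan says.** Section 4.2.2 lists six conditions for a qualifying migraine. The only one about medication is the sixth: "No anti-migraine rescue medication has been taken since the beginning of the migraine headache". The fourth looks back two days, but for headaches and not for drugs: "No other migraine headache or headache has occurred in the previous 48 hours".

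Inclusion criterion 2 (section 5.1) admits migraine with or without aura, apart from aura without headache and the hemiplegic and brainstem forms. At baseline the patient notes "if there is any aura with the qualifying migraine attack". The baseline diary list in section 4.2.2 otherwise covers pain grade, associated symptoms and the most bothersome symptom. It has no medication item.

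The other medication rules begin at the session or later:

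- Section 4.2.2: "Patients will be instructed NOT to take any anti-migraine rescue medication during the 2-hour treatment session". Section 6.6 repeats this.
- Section 4.2.3, 24-hour diary entry: "the rescue medication intake, if any, between 2 hours and 24 hours after the beginning of the treatment session".
- Section 7.1: the patient records whether he or she "took ANY anti-migraine rescue medication during the 24 hours following the beginning of the e-TNS treatment session". Section 6.6 uses the same 24-hour span, and the table in 7.1 marks rescue intake only in the 24-hour column.

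In section 8.2.4, the first condition for the mITT analysis is "The patient treated a qualifying migraine". Medication enters the mITT definition only through that condition. Neither primary outcome in section 3.1 has a medication condition.

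**The concern.** Criterion 6 and the in-session ban show that the 2-hour outcomes are meant to be read without acute medication on board. For a patient with aura, the attack can begin before the headache does. Suppose the patient takes usual acute medication during the aura, then develops Grade 2 pain with an associated symptom and starts the device. None of the six conditions is breached. If the drug takes effect during the session, a pain-free or symptom-free result at 2 hours is credited to whichever device the patient holds.

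Two things are at stake. Response rates would rise in both arms for a reason unrelated to stimulation, which shrinks the difference. And because the document asks for no record of medication before the session, such attacks could not be identified afterwards, so no sensitivity analysis could show whether they mattered. The second loss cannot be repaired once the diaries are collected.

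**Working it through.** **Does another rule close the gap?**

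| Time of intake | Rule that bars it | Where it is recorded |
|---|---|---|
| During aura, before headache | none | nowhere listed |
| Headache start to session start | criterion 6 (4.2.2) | no diary item listed |
| Session, 0–2 h | ban (4.2.2, 6.6) | 24-hour span in 6.6 and 7.1 |
| 2–24 h | conditional permission (4.2.3, 6.6) | 4.2.3, 6.6, 7.1 |

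The first row is open. Criteria 1, 3 and 5 narrow it: the headache must have reached Grade 2 or 3, be less than four hours old, and not already be easing. A patient whose early drug has visibly worked is therefore out. A patient whose drug has not yet worked at baseline is still in. The wake-up footnote to criterion 3 may widen the row slightly. If its onset rule is carried over to criterion 6, a drug taken earlier in the night also precedes the counted start.

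**The plan's own figure.** Inputs from section 8.2.1: verum 35.4%, sham 22.0%, power 90%, 5% level (two-sided per 8.2.3). The pooled-variance formula without continuity correction gives 238 per group, against 239 stated. At n = 239:

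- Power = Φ[(d − 1.96·SE0)/SE1]
- d = 0.354 − 0.220 = 0.134 and mean rate = 0.287
- SE0 = √(0.287 × 0.713 × 2/239) = 0.0414
- SE1 = √[(0.354 × 0.646 + 0.220 × 0.780)/239] = 0.0409
- Power = Φ(1.29) = 90.2%

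The 20% loss allowance gives 239/0.80 = 299 per group, as stated. The plan's figures reproduce and are not in dispute.

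**Effect of affected attacks.** Let f be the share of mITT attacks medicated before the headache and r their 2-hour pain-free rate. Take both as equal in the two arms, with no added device effect in these patients.

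- Verum rate = (1 − f) × 0.354 + f·r
- Sham rate = (1 − f) × 0.220 + f·r
- Difference = (1 − f) × 13.4 points, whatever r is

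The documents give neither f nor r. Assumed: aura in 20–35% of treated attacks, 5–20% of those patients medicating before the headache, and r from 22% to 50%. Then f runs from 0.20 × 0.05 = 1% to 0.35 × 0.20 = 7%.

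| f | Difference (points) | Power, attacks kept (239 per group) | Power, attacks left out |
|---|---|---|---|
| 0 | 13.4 | 90.2% | – |
| 1% | 13.3 | about 89.6% | 89.9% (239 × 0.99 = 236.6) |
| 7% | 12.5 | 84.5–85.9% | 88.0% (239 × 0.93 = 222.3) |

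The range at 7% comes from r: 85.9% at r = 22% and 84.5% at r = 50%. Leaving the attacks out therefore gains about 0.3 points of power at f = 1% and 2.1 to 3.5 points at f = 7%.

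**Wider range.** At f = 10% the difference is 12.1 points and power 82–84% (86.9% if left out). At f = 20% it is 10.7 points and 70–75% (82.8% if left out). With aura in 35% of attacks, f = 20% would need 0.20/0.35 = 57% of aura patients to medicate before the headache.

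**Direction.** If the device has no effect, both arms have the same rate p in unaffected attacks. Both then become (1 − f)p + f·r, and the expected difference stays at zero.

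The same dilution would apply to freedom from the most bothersome symptom. The documents give no sham rate for it, so its power is not computed.

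**The case against.** The strongest reply is that the effect is small and rests on assumed rates. That stands. The net power gain from leaving these attacks out is at most about 3.5 points in the main range, and that needs the top of every assumption at once.

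A reader might infer that the gap favours the device, because a pre-medicated patient can be counted as a success. The documents do not support that. Allocation is randomised and blinded (sections 4.1 and 7.2), so a pre-medicated sham patient counts just as readily. Dilution works against the device. Chance imbalance could go either way, as for any baseline factor, and the test's error rate already allows for it.

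A reader might also infer that the plan sets out to measure the device alone on an unmedicated attack. Section 2 uses neither term. The intent has to be drawn from criterion 6 and the in-session ban.

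Nor should the wording be read as a deliberate two-clock system. The document grades attacks in sections 4.1 and 5.1 and headaches in section 4.2, using the terms loosely. The sponsor may have meant the whole attack. Even so, the text names the headache, and a patient or site applying it as written would pass the aura case.

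Finally, the diary and case report form themselves are not reproduced in the document. One of them could carry a medication question that the protocol does not list. If so, the recording part of this point falls away and the definition part remains.

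**Conclusion.** The gap is real on the text: medication taken during aura, before the headache, is not barred, is not listed for recording, and does not keep the attack out of the mITT set. Its expected consequence is a modest loss of sensitivity. Under assumed contamination of 1–7% with no device effect in those attacks, the loss against the planned 90.2% power is about 0.6 points at the low end and 4.3 to 5.7 points at the high end. If the device does help such patients, the loss is smaller. The figures depend on assumed frequencies that the documents can neither confirm nor exclude. Since the plan has almost no slack above 90%, even a small share takes power below target. There is no basis for calling this bias towards the device or for questioning the sample-size arithmetic. Severity: low (consider). The main reason to act is that the missing information costs little to collect and cannot be recovered later.

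**What to change.** Four linked changes:

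1. For the efficacy analysis, define the criterion 6 look-back as starting at the onset of the treated attack, including any aura.
2. Add one baseline diary item: any anti-migraine medication taken before the session, with drug and clock time. Because it is completed before stimulation starts, it cannot depend on the 2-hour response.
3. Apply the definition in mITT condition 1 using that item. Recording alone would not be enough, since the present wording would still pass these attacks.
4. Pre-specify a sensitivity analysis that reports both primary outcomes with such attacks included and excluded.

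These changes define which attacks count for efficacy. They do not set what a patient may take, which remains for the sponsor and investigators. The look-back should rest on aura, which the diary already records, and not on vaguer early symptoms that the document neither defines nor collects.

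The cost is one phrase, one diary line and one extra analysis. A few attacks would no longer qualify, and the evaluable sample would shrink slightly: by about 2 per group at 1% and 17 per group at 7% of 239.

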#### 4.2.3. Post-treatment phase

Starting two hours after the beginning of the treatment session, the patient is allowed to take anti-migraine rescue medication if and only if the migraine headache pain is moderate or severe, either because there has not been pain relief or because after initial pain relief (no headache or mild headache pain) a moderate or severe headache is resuming.

The patient will have to report the following data in his/her diary at 24 hours after the beginning of the treatment session (24-hour data):

- the rescue medication intake, if any, between 2 hours and 24 hours after the beginning of the treatment session, and, if applicable, the time when the medication was taken
- the headache pain severity on the following scale: 0 = no pain; 1 = mild pain; 2 = moderate pain; 3 = severe pain

- the migraine-associated symptoms (photophobia, phonophobia, nausea, vomiting)

In his/her AE reporting form, the patient will record any adverse event occurring during the 24 hours following the beginning of the treatment session and is instructed to notify the investigator immediately for any serious adverse event with the stimulation.

#### 4.2.4. Final visit

The patient will be instructed to return to the investigation site within approximately 4 days after the treatment session to return the study material, i.e. the Cefaly® Abortive Program device as well as completed paper diary and AE reporting form. The investigator will review the diary in details to ensure data completeness and accuracy (to avoid any missing data, unclear data or discrepancies). If necessary, the investigator will instruct the patient to make him/herself corrections and to sign the corrections with his/her identification (screening) number and the date (no initials).

All adverse events reported on the AE reporting form will be reviewed by the investigator to assess severity. The investigator will also ask the patient if he/she has experienced any adverse effects not reported on the form. Additionally, the investigator will ask the patient if he/she has experienced any device defects.

If a patient has not treated a migraine attack within two months following the screening visit, the study material (Cefaly® Abortive Program device with accessories) will have to be returned to the study site. This will be considered as a protocol violation.

#### 4.2.5. Discontinuation

##### Premature withdrawal of the trial

Patients may withdraw their consent at anytime during the study. If a patient wishes to discontinue from the study but no discontinuation visit is performed (e.g., patient refuses to return to the study site), then the patient should be formally discontinued from the study on the day the decision to discontinue is made. Patient withdrawal may be due to AE and/or SAE or upon patient request.

